UCLA – University of California Los Angeles
UHCMC – University Hospitals of Cleveland Medical Center

STUDY SYNOPSIS AND SCHEMA

| | |
|---|--|
| Protocol Number: | 2894 |
| Protocol Title: | N-carbamylglutamate in the Treatment of Hyperammonemia: Accelerating the Resolution of Hyperammonemia and Clinical Recovery and Safety |
| Study Chair: | [name] [name] |
| Statistician: | [name] |
| Consortium: | N-carbamylglutamate Consortium (NCGC) |
| Participating Sites: | Boston Children's Hospital (BCH), University Hospitals of Cleveland Medical Center (UHCMC), The Children's Hospital of Colorado (CHCO), the University of California Los Angeles (UCLA), Children's Hospital of Philadelphia (CHOP), Lucile Packard Children's Hospital at Stanford (SU), Children's National Hospital (Children's National), Children's Hospital Pittsburgh (UPMC), and Mount Sinai Hospital (MSSM). |
| Activation Date: | July 2 nd , 2012 |
| Sample Size: | 36 patients experiencing approximately 114 hyperammonemia episodes across diagnoses (with approval to enroll up to 80 patients to allow for dropouts, losses to follow-up, and lower than expected incidence of hyperammonemic episodes) |
| Target Enrollment Period: | 5 years |
| Study Design: | Phase II |
| Primary Study Objective: | The overall objective of this project is to determine whether treatment of acute hyperammonemia with N-carbamyl-L-glutamate (N-carbamylglutamate, NCG, Carglumic acid, Carbaglu) in propionic acidemia (PA), methylmalonic acidemia (MMA), late-onset CPS1 deficiency (CPSD) and late-onset Ornithine transcarbamylase deficiency (OTCD) accelerates the resolution of hyperammonemia. |

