| Statistical Considerations (sample size and analysis plan): | Based on 2-tailed testing assuming a type 1 error of 5% and using comparisons of treatment effects across episodes, a sample size of 36 patients, experiencing an average of <4 episodes each (total 114 episodes) would provide 80% power to detect hazard ratio at least as large as 1.7 favoring a higher average probability of the composite outcome in the NCG group. A sample size of 80 will allow for drop outs, losses to follow-up, and lower than expected incidence of hyperammonemic episodes. |
| Sponsors (federal, state, foundation and industry support): | National Institutes of Health (NIH), Recordati Rare Diseases |

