1.2 Study Rationale

As described above, current drug therapy for inherited hyperammonemia relies mainly on the activation of alternate pathways for nitrogen elimination. In contrast, N-carbamylglutamate (NCG), a stable analog of N-acetylglutamate, catalytically stimulates the urea cycle, thus converting many more molecules of ammonia to urea with a relatively small dose of the drug. This represents a paradigm shift in the medical treatment of hyperammonemia.

A drug that could repair or stimulate a dysfunctional urea cycle would have several advantages over current therapy. First, it would intervene through the normal pathway of ureagenesis, which is catalytic rather than stoichiometric. Second, it may not need to replace current treatment but would be complementary to it. Third, the ability to stimulate residual ureagenesis could benefit many conditions that cause hyperammonemia, not just a single disorder. Enhancement of residual ureagenesis capacity in patients with hyperammonemia would markedly alter the natural disease course resulting in a manageable phenotype and better clinical outcome.

Our recent studies show that ureagenesis is augmented by NCG in healthy individuals and in more than half of all individuals with inborn errors that were tested.

The eligibility for the studies in this study specifically includes severe PA and MMA and “milder” CPSD and OTCD, which may appear paradoxical. However, the rationale for these selection criteria is based on the different mechanism(s) of action in these disorders. Significant hyperammonemia in PA or MMA is usually seen only in the most severely affected patients who present as newborns. Patients with hypomorphic alleles have milder disease and are unlikely to have serious hyperammonemia.⁷² In severely affected patients with PA and MMA, NCG works to alleviate deficiency of NAG created by the inhibition of NAGS by the mitochondrial accumulation of propionyl-CoA, hence, the more profound the NAG deficiency, the more robust the NCG effect. In CPSD and OTCD however, the putative effect of NCG relies on stimulating residual CPS1 or OTC activity. Indeed, when these enzymes are totally absent, no amount of NCG would help, hence, the need to enroll patients with partial rather than complete enzyme deficiencies.

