We propose to use Cox Proportional Hazard modeling to implement the primary analysis to compare the average differences in time to reach the composite outcome and allow us to control for differences in severity (ammonia level and or FSS) at episode baseline. This method will also allow us to take account of and adjust statistical testing for the correlation between results of participants who contributed more than one event to the analysis. The comparison of slopes of the ammonia decline curves by treatment group will shift to secondary analysis, which will allow us to focus on consistency of results rather than choosing the precise model for significance testing for the purpose of rejecting the null hypothesis of no treatment effect.

Study analyses will be based on an intention-to-treat paradigm. In analyzing the primary outcome, we will evaluate the difference over time in the probability of reaching an ammonia level of 50 $\mu\text{mol/L}$ or hospital discharge. For this purpose, we will use a z-test to assess the evidence that the hazard (event) ratio (HR) differs from 1 (no effect) to test for a difference in the probability of the composite outcome over time by the group. We will account for the correlation between repeat episodes per participant by treating participant episodes with the same ID as a cluster, which will adjust standard error estimates for the intraclass correlation between episodes in the same cluster. The primary analysis will be implemented using the sts cox procedure in Stata 14 (StataCorp. *Stata Statistical Software: Release 14*, College Station, TX: StataCorp LP, 2015).

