8.3.1 Interim Analysis

In addition to the proposed final analysis, we will conduct an interim analysis using the same methodology described above when at least 50% (70 episodes) or when at least 60 episodes have occurred after the study midpoint based on the projected 4 hyperammonemic events per participant have been completed (participant discharged). Allowing for one interim look for both efficacy and futility when half the information becomes available, using an O'Brien-Fleming stopping rule and a Lan-DeMets approach to the use function of the p-value. If conducted exactly at the 50% outcome, the boundary for rejecting the null hypothesis and concluding that Carbaglu is either efficacious or worse than placebo is a z-score of $+/-.2.9626$, corresponding to a p-value <0.0031 at the interim look. The boundary for deciding futility, i.e., that Carbaglu is not expected to be significantly different than placebo is $+/-.3557$, corresponding to a p-value of >0.72 at the interim look. With these boundaries, the decision rules at the conclusion of the study will be $+/-.1.9686$ or more extreme to conclude that Carbaglu is either efficacious or worse

than placebo, corresponding to a p-value of <0.049. These values were calculated using East 5.3 (Cytel, Inc.).

A report of the interim analyses will be provided to the DSMB, which will review and discuss the results considering all evidence available, including magnitude of difference between groups and p-value, as well as results on secondary outcomes and safety to consider whether the results warrant stopping the trial either from persuasive evidence of benefit or harm.

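### With about 36 patients, the z-test on a patient-clustered Cox standard error rejects more often than its stated levels, and no small-sample method is specified

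*Combined protocol and SAP*

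**What the plan says.** Section 8.3 (Statistical Considerations) states of the primary analysis: "we will use a z-test to assess the evidence that the hazard (event) ratio (HR) differs from 1". Repeat episodes are handled "by treating participant episodes with the same ID as a cluster, which will adjust standard error estimates". The same clustered Cox method is used for the secondary time-to-discharge comparison.

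Section 8.3.1 (Interim Analysis) says "we will conduct an interim analysis using the same methodology described above". It gives normal boundaries of 2.9626 (p < 0.0031) at the interim and 1.9686 (p < 0.049) at the end, and ties the interim value to one information fraction: "If conducted exactly at the 50% outcome, the boundary for rejecting the null hypothesis". The look is triggered "when at least 50% (70 episodes) or when at least 60 episodes have occurred".

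The number of clusters comes from the synopsis, which plans "36 patients experiencing approximately 114 hyperammonemia episodes across diagnoses" and allows up to 80 patients. Section 8.4 allows for clustering only through an R-square of 0.05 in the sample-size calculation, which does not alter the test. The documents name no bias-corrected standard error, t reference, degrees of freedom or permutation test.

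**The concern.** A patient-clustered (sandwich) standard error is justified when there are many clusters. With few, unequal clusters two things go wrong. The estimator is too small on average, because fitted residuals understate the true variation. It is also noisy, so the ratio has heavier tails than a normal. Both push the rejection rate up.

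This is the only primary efficacy test, and its final decision rule is a fixed threshold. If the statistic is not close to standard normal, the stated 0.0031, 0.049 and overall 5% levels do not describe it. A false finding of benefit or harm becomes more likely than stated, and the DSMB receives an interim p-value that looks stronger than it is.

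The clustering itself is not the fault. Section 1.2 reports that ureagenesis was augmented "in more than half of all individuals with inborn errors that were tested", and section 1.3.2.2 reports improvement in some CPSD patients. The team therefore has reason to expect the drug effect to differ between patients. The fault is the large-sample reference.

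**Working it through.** **1. Reproduce the plan's boundaries.** Lan-DeMets O'Brien-Fleming-type spending, 0.025 per side, one look at fraction t: one-sided alpha spent = 2[1 − Φ(z(0.9875)/√t)]. The final boundary is solved from the bivariate normal with correlation √t.

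| Interim at | t | Interim z (p) | Final z (p) |
|---|---|---|---|
| 57 of 114 | 0.500 | 2.9626 (0.0031) | 1.9686 (0.0490) |
| 60 of 114 | 0.526 | 2.877 (0.0040) | 1.971 (0.0487) |
| 70 of 114 | 0.614 | 2.633 (0.0085) | 1.983 (0.0473) |

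The first row matches section 8.3.1. The boundaries are computed correctly for a standard normal statistic. The question is whether the planned statistic is one.

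**2. Simulate the planned test under no effect.** The statistic is z = β̂ / SE, where SE² comes from the score-residual sandwich summed within patient, multiplied by G/(G − 1), and G is the number of contributing patients.

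- From the documents: 36 patients, 114 episodes (114/36 = 3.2 per patient), 9 sites, episode-level randomization stratified by site, adjustment for baseline severity, no censoring (section 8.4).
- Assumed: blocks of 4; one baseline covariate; at least one episode per patient, the rest spread by gamma propensities (shape 1 or 3); gamma frailty variance 0, 0.5 or 1 for within-patient correlation.
- 10,000 null trials per setting. Monte Carlo SE near 7% is √(0.07 × 0.93/10,000) ≈ 0.25 points; near 1% it is about 0.1 points.

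Final look, 36 patients, P(|z| > 1.9686), nominal 4.9%:

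| Episode spread | Frailty 0 | 0.5 | 1 |
|---|---|---|---|
| shape 1 | 6.57% | 7.36% | 7.89% |
| shape 3 | 6.24% | 7.40% | 7.88% |

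Other results with the clustered z-test:

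| Quantity | Nominal | Simulated |
|---|---|---|
| Interim, z 2.9626, 57, 60 or 70 episodes, 36 patients | 0.31% | 0.8-1.1% |
| Interim, z 2.877, 60 of 114, 36 patients | 0.40% | 0.95-1.24% |
| Interim, z 2.633, 70 of 114, 36 patients | 0.85% | 1.7-2.2% |
| Overall, two looks, 36 patients | 5% | 6.6-8.4% |
| Overall, futility rule also applied, 36 patients | 5% | 6.3-7.9% |
| Final, 60-80 patients | 4.9% | 5.8-7.0% |
| Interim, 57 episodes, 60-80 patients | 0.31% | 0.6-0.9% |
| Overall, 60-80 patients | 5% | 6.1-7.4% |

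With 36 enrolled, a mean of only 27.5-29.0 patients had contributed by 57 episodes and 30.2-31.5 by 70.

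**3. Check with a separately coded simulation.** This varied the spread of episodes (even, skewed, very skewed), the number of covariates and the G/(G − 1) factor. With 36 patients the final level was 5.8-8.7%. The interim level was 0.56-1.07% with all 36 contributing and 0.92-1.72% with only 18-22. Since 0.56/0.31 = 1.8 and 1.07/0.31 = 3.5, the 36-patient interim excess is about 2 to 3.5 times nominal.

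**4. Locate the cause.** On the same 36-patient final data, the unclustered model-based test rejected 3.6-5.6%. The excess therefore comes mainly from the clustered standard error.

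**5. Candidate corrections, 36 patients.** A t reference with 35 df (critical value 2.040 for p = 0.049) plus G/(G − 1) gave 5.5-6.9% at the final look, so it is only a partial repair. A jackknife standard error with t(G − 1) gave 4.4-4.8% at the final look in one set of runs and about 5.5% in another. At the interim it gave 0.13-0.28% at 57 episodes (nominal 0.31%) and 0.43-0.72% at 70 (nominal 0.85%).

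**6. Should clustering be dropped?** With patient-varying effects (mean log-HR 0, SD 0.7), rejection was:

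| Frailty | Unclustered z | Clustered z | Jackknife-t |
|---|---|---|---|
| 0.5 | 9.0% | 8.6% | 5.2% |
| 0 | 15.0% | 11.5% | 8.0% |

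The marginal HR may not be exactly 1 here, so these figures are only indicative. They give no support for removing the clustering.

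**The case against.** The strongest objections concern size and remedy.

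- **Frailty.** Most of the upper range uses frailty variance 0.5-1, while section 8.4 calls the clustering effect modest. With little frailty (0 to 0.25) the final level is about 6.5%. This stands as a caution on the upper end. However, very uneven episode counts with no frailty gave 8.2-8.7%, so strong correlation is not required.
- **Tied times.** Ammonia is measured every 6-12 hours and then daily, so event times will be tied. Grouping times at 12- and then 24-hour steps gave 6.0-6.3% with 36 patients in one check, 5.5% with 60 patients, and 5.9% with 70 patients. The excess shrinks but remains.
- **Up to 80 patients.** More clusters help, but 60-80 patients still gave 5.8-7.0% without ties.
- **Interim mistiming.** Comparing looks at 60 or 70 episodes with 0.31% mixes late timing with cluster bias. Against the correct levels the ratios are about 2.4-3.1 and 2.0-2.6, so an excess of at least twofold remains.
- **The remedy over-corrects and costs power.** The jackknife-t is conservative at the interim, and gave 4.0% at the final look with 80 patients. The power loss is real. This bears on which method to choose, not on whether one is needed.
- **Heterogeneity evidence.** The cited responses concern ureagenesis and metabolites, not the composite endpoint. That weakens, without removing, the argument for clustering.
- **Limited consequences.** This is a Phase II trial and the DSMB weighs other evidence, so crossing the interim boundary does not stop it automatically. The p-value it receives is still miscalibrated.

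**Conclusion.** The concern holds. The boundaries are correct for a normal statistic, but the planned statistic is not close enough to normal with about 36 clusters. Under the stated assumptions the final test rejects about 6-8% under the null instead of 4.9%. The interim test rejects about 2 to 3.5 times as often as 0.31%, and the overall error is about 6.6-8.4% instead of 5%. Applying the futility rule removes only about 0.3-0.6 points of that.

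The direction and the absence of a small-sample method are firm. The exact percentages depend on episodes per patient, within-patient correlation, block size and ties, which the documents do not give. The mildest checks, with more patients and tied times, came down to 5.5%. The plan should be corrected before unblinding.

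**What to change.** Keep the Cox model, the hazard ratio, clustering by patient and the boundaries. Pre-specify one small-sample method for the p-value and the confidence interval at both looks. Example wording:

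> The treatment log hazard ratio will be tested using a delete-one-patient jackknife standard error referred to a t distribution with (contributing patients − 1) degrees of freedom; the 95% confidence interval uses the same standard error and reference. The two-sided p-value is compared with 0.0031 if the interim falls at exactly 50% information, or with the Lan-DeMets level at the actual fraction (0.0040 at 60/114, 0.0085 at 70/114), and at the end with the matching final level (0.049, 0.0487 or 0.0473).

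Before unblinding, confirm these levels by simulation using the blinded distribution of episodes per patient and the real measurement schedule. Another small-sample method is acceptable if it holds the levels in that simulation. A re-randomization test following the site-stratified episode schedule can be added as a supporting check; it needs the generating algorithm and block sizes, not only the stored list. Apply the same correction to time to discharge.

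The cost is SAP wording, a short program and one simulation, with no new data. Intervals widen by about 11-13%. Power at HR 1.7 with 114 episodes and 36 patients falls from 79% to 72% with no within-patient correlation (about 77% to 71% in another run). Part of the higher figure was excess false positives. At 146 episodes, the number section 8.4 gives for HR 1.6, jackknife-t power at HR 1.7 is 83%; that is 32 more episodes (32/114 = 28%). The power statement should be restated for the chosen method, whether or not the target changes.

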8.3.1 Interim Analysis

In addition to the proposed final analysis, we will conduct an interim analysis using the same methodology described above when at least 50% (70 episodes) or when at least 60 episodes have occurred after the study midpoint based on the projected 4 hyperammonemic events per participant have been completed (participant discharged). Allowing for one interim look for both efficacy and futility when half the information becomes available, using an O'Brien-Fleming stopping rule and a Lan-DeMets approach to the use function of the p-value. If conducted exactly at the 50% outcome, the boundary for rejecting the null hypothesis and concluding that Carbaglu is either efficacious or worse than placebo is a z-score of $+/-.2.9626$, corresponding to a p-value <0.0031 at the interim look. The boundary for deciding futility, i.e., that Carbaglu is not expected to be significantly different than placebo is $+/-.3557$, corresponding to a p-value of >0.72 at the interim look. With these boundaries, the decision rules at the conclusion of the study will be $+/-.1.9686$ or more extreme to conclude that Carbaglu is either efficacious or worse

than placebo, corresponding to a p-value of <0.049. These values were calculated using East 5.3 (Cytel, Inc.).

A report of the interim analyses will be provided to the DSMB, which will review and discuss the results considering all evidence available, including magnitude of difference between groups and p-value, as well as results on secondary outcomes and safety to consider whether the results warrant stopping the trial either from persuasive evidence of benefit or harm.

8.4 Rationale for Sample Size and Statistical Power

All sample size and power estimates are based on 2-tailed testing, which assumes a type 1 error of 5% and achieving 80% power to detect an HR difference by treatment group and that there is no censoring as each episode will contribute information to one of the composite outcomes. We used the Cox Regression procedure in PASS (Hintze, J. PASS 11. NCSS, LLC. Kaysville, Utah, USA. www.ncss.com, 2011) to evaluate the composite time to event outcome of the earlier of the time to reach an ammonia level of 50 μ mol/L or time to discharge within hyperammonemic episodes (the unit of randomization and analysis). We evaluated HR estimates above 1, reflecting that the NCG group achieved the higher probability of achieving the composite event. Based on these considerations, a total sample size of N=146 episodes can detect an HR of 1.6, one of N=114 can detect an HR of 1.7, one of N=93 can detect an HR of 1.8 and one of N=78 can detect an HR of 1.9. These sample size estimates account for an inflated R-square as large as 0.05 between the time to event outcome and covariates reflecting baseline severity at the start of an episode. We used the inflated R-square to account for the modest effect of clustering of episodes within a person. Therefore, we consider the originally-targeted sample size of 144 episodes to be more than sufficient to meet the aims of the study. Based on our re-analysis of the time-to-event outcome, an HR of 1.7 is realistic and a sample size of 114 episodes is sufficient to detect that effect. Therefore, the target sample size will be 114 episodes.

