10.3.4 REDCap Randomization

At each episode, online checks ensure all episode eligibility criteria are met, and if so, access is provided to the REDCap randomization button. When pressed, the button implements an online program that accesses a pre-generated, encrypted, randomization schedule created by the CNMC Division of Biostatistics and Study Methodology to make the appropriate treatment assignment for that subject. This procedure will provide a balanced allocation of assignments to each treatment arm over the episodes. Once an assignment is made, to maintain the blind the person enrolling the subject will be notified simply that the site pharmacy is preparing the assigned medication. These procedures will ensure tamper-proof, blinded randomization as well as overall balance in assignment to treatment groups. The Site Pharmacy will simultaneously receive online or fax notification of the assignment and will be requested to prepare the appropriate dosing kit for pick-up or delivery to the floor (depending on site logistics).

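### Section 8.4 says its sample sizes allow for an R-square up to 0.05, but at 0.05 the formula gives 150/118/96/81 episodes, not the printed 146/114/93/78

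*Combined protocol and SAP*

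**What the plan says.** Section 8.4 gives the basis of the calculation: "All sample size and power estimates are based on 2-tailed testing, which assumes a type 1 error of 5" percent, "achieving 80% power to detect an HR difference by treatment group", no censoring, and the Cox regression procedure in PASS 11. It lists four episode totals: 146 for HR 1.6, then "one of N=114 can detect an HR of 1.7, one of N=93 can detect an HR of 1.8", and 78 for HR 1.9. It adopts 114 as the target.

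Two sentences describe what these totals contain. The first is "These sample size estimates account for an inflated R-square as large as 0.05 between the time to event outcome and covariates", where the covariates are those for severity at the start of an episode. The second is "We used the inflated R-square to account for the modest effect of clustering of episodes within a person".

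Three other places bear on the check. Section 10.3.4 says randomization gives a "balanced allocation of assignments to each treatment arm over the episodes". Section 8.3 treats each participant's episodes as a cluster, "which will adjust standard error estimates for the intraclass correlation between episodes in the same cluster". Section 8.3.1 plans one interim look for both efficacy and futility and prints its boundaries.

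**The concern.** Section 8.4 prints enough inputs to re-run the calculation. A reader who does so at the stated R-square of 0.05 gets 118 episodes for HR 1.7, not 114, and the other three totals fail in the same direction. So the text and the numbers were not produced with the same R-square.

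This matters because 114 is the trial's target and 8.4 is its only justification. The section tells the reader that the target holds a margin of a given size and that this margin also absorbs the effect of repeat episodes. The margin is smaller than stated, and it is not built from anything that measures clustering.

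**Working it through.** **Inputs.** From 8.4: two-sided 5% (z = 1.960), 80% power (z = 0.8416), event fraction 1 because no censoring is assumed, and HR 1.6, 1.7, 1.8 and 1.9. Allocation is taken as 1:1 (p = 0.5) from the balanced allocation in 10.3.4, since 8.4 gives no ratio. The documents do not print the formula, so the standard one for Cox regression is assumed:

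N = (1.960 + 0.8416)² / [p(1−p) × (ln HR)² × (1 − R²)], with (1.960 + 0.8416)² = 7.849 and p(1−p) = 0.25.

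**Example, HR 1.7.** (ln 1.7)² = 0.2816, so N at R² = 0 is 7.849 / (0.25 × 0.2816) = 111.50. At R² = 0.05 it is 111.50 / 0.95 = 117.37, rounded up to 118.

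**Reproducing the plan's figures, then applying the stated R-square.**

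| | HR 1.6 | HR 1.7 | HR 1.8 | HR 1.9 |
|---|---|---|---|---|
| Printed in 8.4 | 146 | 114 | 93 | 78 |
| R² = 0 | 142.12 | 111.50 | 90.87 | 76.21 |
| R² = 0.02 | 145.02 | 113.78 | 92.73 | 77.76 |
| R² = 0.02, rounded up | 146 | 114 | 93 | 78 |
| R² = 0.05 | 149.60 | 117.37 | 95.65 | 80.22 |
| R² = 0.05, rounded up | 150 | 118 | 96 | 81 |
| Shortfall of printed N | 4 | 4 | 3 | 3 |

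All four printed values appear together for R² between 0.0199 and 0.0219 if N is rounded up, and between 0.0233 and 0.0261 if N is rounded to the nearest whole number.

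**Largest R² at which the printed N still gives 80% power**, that is 1 − N(R² = 0) / N(printed):
- HR 1.6: 1 − 142.12/146 = 0.027
- HR 1.7: 1 − 111.50/114 = 0.022
- HR 1.8: 1 − 90.87/93 = 0.023
- HR 1.9: 1 − 76.21/78 = 0.023

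**Other explanations tried at R² = 0.05.**
- Rounding to nearest gives 150/117/96/80.
- Allocation of 55:45 gives 152/119/97/82, and 60:40 gives 156/123/100/84. Equal allocation gives the smallest N, and any censoring would raise it further.
- The Freedman form gives 156/123/102/86.
- One-sided testing gives 118/93/76/64.
- Alpha 0.049 gives 151/119/97/81.
- Dividing by √0.95 instead of 0.95, with rounding to nearest, does return the printed set (145.82/114.40/93.23/78.19), but that is not the standard formula.

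**Power of the target: 114 episodes, HR 1.7.** In a fixed design, power = Φ(√(114 × (1 − R²) × 0.25) × ln 1.7 − 1.960). At R² = 0.05 this is Φ(2.761 − 1.960) = 0.788. The sequential figures use the boundaries printed in 8.3.1 (efficacy ±2.9626 at the look and ±1.9686 at the end, futility ±0.3557), with the look at exactly half the information.

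| | Fixed design | With efficacy look | Efficacy look and binding futility |
|---|---|---|---|
| R² = 0 | 80.9% | 80.7% | 79.7% |
| R² = 0.05 | 78.9% (0.7885) | 78.7% | 77.7% |

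At R² = 0.05 in a fixed design, 114 episodes have 80% power at HR 1.713.

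**The clustering sentence.** The only place R² enters is the factor 1/(1 − R²). That factor holds no number of episodes per person and no within-person correlation, so it cannot represent their effect.

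**The case against.** The strongest reply is that nothing of substance turns on this. The gap is 3 to 4 episodes, about one point of fixed-design power, and no boundary, estimate or decision rule changes. That is right, and it limits the point to a correction of 8.4.

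A second reply is that wording such as up to 0.05 is only a ceiling. It does not help: a ceiling of 0.05 still says that the sizes hold their power at 0.05, and they stop doing so between 0.022 and 0.027.

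Several stronger readings are tempting, and the documents do not support them:
- **That 114 contains no allowance at all.** The formula needs 112 at R-square 0, and all four printed totals exceed their R-square 0 values (143/112/91/77). An allowance is present; it is smaller than stated.
- **That the value used was 0.02.** Two ranges of R-square fit all four totals, depending on rounding, and the software output is not in the documents.
- **That the 80% power in the synopsis is refuted, or that it is confirmed.** At R-square 0 the target gives 80.9% in a fixed design, 80.7% with the efficacy look, and 79.7% if the futility boundary is binding. Section 8.3.1 does not say whether it is. None of these figures includes clustering.
- **That clustering leaves the trial short of power.** Episodes of the same person are randomized separately, so within-person correlation could raise or lower the variance of the treatment effect. That was not calculated here.

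It is also fair to say that the cluster-adjusted standard errors in 8.3 already address inference. The criticism concerns what 8.4 claims about sample size, not the planned test.

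**Conclusion.** The mismatch is real. Under the inputs of 8.4, an R-square of 0.05 requires 150/118/96/81 episodes, and the printed 146/114/93/78 correspond to about 0.02 to 0.026. Keeping 114 episodes with an R-square of 0.05 at HR 1.7 means about 78.9% power in a fixed design, 78.7% with the efficacy look and 77.7% if futility is binding. The description of the R-square as an allowance for clustering is also unsupported.

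The conclusion rests on two assumptions: 1:1 allocation, and that the PASS procedure uses the standard formula. Departing from the first only widens the gap. The second is supported by the match of all four printed values at a single R-square. The sequential figures further assume a look at exactly half the information. No conclusion is drawn about whether enrolment should change, because the effect of clustering on power is unquantified.

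**What to change.** Change section 8.4 in two places.

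1. Make the R-square and the episode totals agree. Either state the R-square actually used, taken from the sponsor's software output, or print 150/118/96/81 for R-square 0.05 and state that 114 episodes give about 79% power at HR 1.7 under that allowance in a fixed design.
2. Replace the clustering sentence. State that the sample size has no separate allowance for clustering, that the effect of clustering on power is unquantified, and that the analysis handles within-person correlation through the cluster-adjusted standard errors of 8.3.

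The cost is two sentences and a look at the saved output. If the 0.05 allowance is kept, the plan must also accept a stated power of about 79% instead of 80% for its target under that allowance.

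### The 80% power stated for 114 episodes is a fixed-sample figure that fits an R-square of 0.02 rather than 0.05 and leaves out the interim look; at 0.05 with the interim it is about 78–79%

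*Combined protocol and SAP*

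**What the plan says.** Section 8.4 gives the basis of the calculation: "All sample size and power estimates are based on 2-tailed testing, which assumes a type 1 error of 5% and achieving 80% power". It uses a Cox regression routine in PASS and assumes that "there is no censoring as each episode will contribute information to one of the composite outcomes", so events equal episodes. The results are listed as "a total sample size of N=146 episodes can detect an HR of 1.6, one of N=114 can detect an HR of 1.7", followed by 93 episodes for a hazard ratio of 1.8 and 78 for 1.9. The section says these sizes allow for an R-square as large as 0.05, which is also meant to cover clustering of episodes within a person. It judges that "an HR of 1.7 is realistic" and that "a sample size of 114 episodes is sufficient to detect that effect", and concludes: "Therefore, the target sample size will be 114 episodes". The synopsis carries the same claim, that the sample "would provide 80% power to detect hazard ratio at least as large as 1.7". Neither place mentions an interim look in connection with power.

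Section 8.3.1 describes that look: "Allowing for one interim look for both efficacy and futility when half the information becomes available". For a look at exactly 50%, it prints an efficacy bound of ±2.9626, a futility bound of ±0.3557 and a final bound of ±1.9686, all computed in East. It gives no power for the design with these bounds.

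**The concern.** The size in 8.4 and the bounds in 8.3.1 come from separate calculations in different software, and nothing connects them. A final bound above 1.96 and a futility stop both take power away from a fixed-sample design, and 114 is the bare minimum under the fixed-sample formula at R-square 0.02. The stated R-square allowance does not fit the printed sizes either. So the one power figure that readers and the DSMB will rely on describes neither the stated allowance nor the design with its interim. What is at stake is the accuracy of that figure, and knowing what the futility bound costs before anyone applies it.

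**Working it through.** **Inputs from the documents.** Two-sided 5%, 80% power, hazard ratio 1.7, 114 episodes, no censoring, R-square up to 0.05 (all section 8.4). Interim bounds 2.9626 and 0.3557, final bound 1.9686, information fraction 0.5 (section 8.3.1).

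**Assumptions.** 1:1 allocation (section 10.3.4 says only that assignment is balanced), and R-square entering as a factor (1 − R²) on the information.

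**Step 1: reproduce the printed sizes.** N = 4 × (1.960 + 0.842)² / [ln(HR)² × (1 − R²)], where (1.960 + 0.842)² = 7.849 from unrounded values. For HR 1.7, ln(1.7) = 0.5306 and its square is 0.2816, so N = 111.50 / (1 − R²). Rounding up:

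| R-square | HR 1.6 | HR 1.7 | HR 1.8 | HR 1.9 |
|---|---|---|---|---|
| Printed | 146 | 114 | 93 | 78 |
| 0 | 143 | 112 | 91 | 77 |
| 0.01 | 144 | 113 | 92 | 77 |
| 0.02 | 146 | 114 | 93 | 78 |
| 0.03 | 147 | 115 | 94 | 79 |
| 0.05 | 150 | 118 | 96 | 81 |

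R-square 0.02 matches all four. The stated 0.05 matches none and would need 118 episodes at HR 1.7.

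**Step 2: fixed-sample power at 114.** Drift θ = ln(1.7) × √[114 × (1 − R²) / 4], and power = Φ(θ − 1.960).
- R-square 0.02: θ = 2.804, power 80.1%.
- R-square 0.05: θ = 2.761, power 78.8%.

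**Step 3: power with the interim.** Z1 (interim) and Z2 (final) are bivariate normal with means θ√0.5 and θ and correlation √0.5.
- Futility enforced: P(Z1 ≥ 2.9626) + P(0.3557 < |Z1| < 2.9626 and Z2 ≥ 1.9686).
- Futility advisory: the same, without the lower limit on |Z1|.

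| R-square | Fixed sample | Interim, futility advisory | Interim, futility enforced |
|---|---|---|---|
| 0 | 80.9% | 80.7% | 79.7% |
| 0.02 | 80.1% | 79.9% | 78.9% |
| 0.05 | 78.8% | 78.7% | 77.7% |

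The efficacy look and the stricter final bound cost about 0.15 point. Enforcing futility costs about 1.0 point more, because it stops 4.2% of trials at R-square 0.02 (4.5% at 0.05) even when the hazard ratio is truly 1.7.

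**Step 4: which futility rule do the bounds imply?** Under no effect, the pair 2.9626 and 1.9686 gives a two-sided type 1 error of 0.0500 if futility is ignored and 0.0482 if it is enforced. The final bound is therefore the one that a non-binding futility rule produces.

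**Step 5: timing.** Half of 114 is 57, but the triggers in 8.3.1 are 70 or 60 episodes. With Lan-DeMets O'Brien-Fleming bounds recomputed for those points and futility held at 0.3557 (an assumption), power with futility enforced is 79.1% (R-square 0.02) and 77.9% (0.05) at 60 of 114, and 79.4% and 78.2% at 70 of 114.

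**The case against.** A reader might infer that the interim look by itself means the trial does not deliver its 80%. The documents do not support that. Most of the interim's cost needs a futility bound that is always obeyed. The printed final bound fits a non-binding rule, and 8.3.1 has the DSMB weigh all the evidence and closes by speaking of stopping for benefit or harm, without naming futility. With futility advisory, power at R-square 0.02 is 79.9%, which any reader would call 80%. The look may also come later than the 50% used here, which reduces the cost of enforced futility a little. And 8.4 names its method and never claims that the 80% includes the interim.

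All of that stands as regards the interim. It does not rescue the figure at the R-square that 8.4 itself states. At 0.05 power is 78.8% before any interim, and 78.7% with the interim and advisory futility. It can be said that "as large as" wording makes 0.05 a ceiling rather than a planning value, but a size said to account for a value up to 0.05 should hold 80% at 0.05. Nor is advisory futility established: 8.3.1 does print a futility boundary as a decision rule, so enforcement remains possible.

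**Conclusion.** Wrong as written, minor. The 80% for 114 episodes is a fixed-sample figure at R-square 0.02. At the stated allowance of 0.05 with the interim included, power for a hazard ratio of 1.7 is 78.7% if futility is advisory and 77.7% if it is enforced.

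The shortfall at 0.05 has two parts. Moving from R-square 0.02 to 0.05 takes 80.1% to 78.8%, about 1.2 points before rounding. The interim takes a further 0.15 point (advisory) to 1.2 points (enforced). With enforced futility the two parts are about equal; with advisory futility nearly all of it is the R-square.

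A reader might also conclude that 114 episodes are too few. A gap of 1 to 2 points does not support that. The result rests on 1:1 allocation, no censoring, a look at half the information, and R-square acting as a factor (1 − R²).

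**What to change.** In section 8.4 and the synopsis, label 114 as a fixed-sample size. Restate power for a hazard ratio of 1.7 at R-square 0.05 with the interim as about 78–79%: 78.7% with advisory futility, 77.7% if the bound is enforced. In 8.3.1, say that the futility bound is non-binding, which is what the printed final bound of 1.9686 implies, so that the DSMB knows its status and its cost of about 1 point.

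This changes wording only. The one cost is a slightly less favourable stated power. No extra enrolment is needed. For reference, holding 80% at R-square 0.05 with both bounds followed would take 121 episodes.
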